3.2 Overall Schedule of Times and Events

The overall schedule of Time and Events is shown in Table 3.2. Note that the timing of each visit depends upon when the subject first received UT-15C SR (e.g. whether the subject was assigned to active or placebo treatment in Protocol TDE-PH-301, TDE-PH-302, or TDE-PH-308). Subjects receiving placebo in the previous study, or subjects enrolled from the TDE-PH-202 study who are beginning a dose of 0.25mg BID, must be contacted weekly by telephone (at a minimum) during the first 12 weeks of the open-label study to ensure subject safety. More specifically, these calls should assess study drug dose titration needs, potential adverse events, concomitant medication usage and PAH signs and symptoms. Monthly telephone calls (at a minimum) must be conducted for all subjects actively participating in TDE-PH-304, regardless of study drug allocation (UT-15C SR or placebo) in the previous study, to assess dose titration needs, potential adverse events, concomitant medication usage and PAH signs and symptoms. In addition to the scheduled study visits, all subjects must be seen in the clinic no less than once every six months for routine standard of care medical evaluation.

Subjects enrolling from the TDE-PH-203 and TDE-PH-205 studies will transition on the same dose they were receiving at the end of the study. Study visits for the TDE-PH-304 protocol will be based on the date the subject first received active UT-15C in their respective preceding study.

Table 3.2. Time and Events

Assessment	Visit ^{4,5,6,7}						
	Visit 0-1 (Weeks 1-12) ³	1	2	3	4	5+ ⁸	EXIT ⁹
Adverse Events	X	X	X	X	X	X	X
PAH Concomitant Medications	X	X	X	X	X	X	X
Concomitant Medications	X	X	X	X	X	X	X
6-Minute Walk Test/Borg Dyspnea Score ¹				X			
Clinical Laboratory Parameters ²		X	X	X	X	X	X
Drug Accountability/Compliance	X	X	X	X	X	X	X

¹ **6-Minute Walk Test/Borg Dyspnea Score** as described in Appendix A. conducted 3 to 6 hours after the morning dose of UT-15C SR.

² **Laboratories** to be collected are described in Appendix B.

³ **Weekly telephone calls** (at a minimum) required during Weeks 1-12 for subjects randomized to placebo in TDE-PH-301, 302, or 308 to assess dose titration needs, potential adverse events, concomitant medication usage and PAH signs and symptoms. Also applies to subjects enrolled from the TDE-PH-202 study who are beginning a dose of 0.25mg BID.

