6.1.1 Twice Daily Dosing Regimen

The next dose of study drug should be taken the following morning. At this time oral dosing of UT-15C SR will be initiated at 0.25 mg twice daily (every 12 hours +/- 1 hour) immediately following (~10 minutes) breakfast and dinner. Subjects must be instructed to take the appropriate amount of 0.25, 0.5, 1, and/or 2.5 mg tablets based upon their given dose. In general, the dose of study drug should be increased in 0.25 to 0.5 mg increments every 3 days, in the absence of dose-limiting drug-related side effects, to ensure the subject receives the optimum clinical dose throughout the study. The 0.125 mg strength, if available, may be used throughout the study if a 0.25 mg dose increase is not tolerated and an intermediate dose is required. Dose changes should be conducted under appropriate medical supervision in consultation with the study site.

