#### **5 SEQUENCE OF PLANNED ANALYSES**

Interim analyses will occur to support regulatory submissions (e.g., NDA, 120-day safety updates, etc.) and as frequently as yearly in order to continuously monitor the long-term safety of oral treprostinil in this ongoing study. For each interim analysis, the data currently in the database will be soft locked by Data Management and provided to Statistics and Programming for creation of output as described in this analysis plan.

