## 11 SAFETY ANALYSES

### 11.1 EXTENT OF EXPOSURE

Study drug exposure will be listed, including subject number, previous study, concomitant medication use, BID to three times daily (TID) transition, exposure (weeks), and categorical exposure (by visit). Exposure is calculated as the time exposed to active study drug. For subjects treated with active drug during the parent study, exposure calculations will include their exposure during the parent study. For subjects treated with placebo during the parent study, exposure calculations will include only the exposure to active drug during the OL study. The summary of disposition and study drug exposure will detail the number (percent) of subjects who died during the study, as well as the study drug exposure both by categorical visits ( $\geq 3$  months,  $\geq 6$  months, etc.) and using descriptive statistics. The total study drug exposure (pt-years) will also be displayed.

Study drug dosing will be summarized at each visit by previous study and overall. The summary will include a categorical summary of current status (in study, death, progression of PAH, AE, consent withdrawn, lost to follow-up, discontinued for other reasons, etc.) and study drug dose (<1 mg, 1-<2.5 mg, 2.5-<5 mg, 5-<10 mg, 10-<20 mg, 20-<30 mg BID/TID), as well as a descriptive statistics summary of study drug dose (mg BID/TID).

Study drug dosing will also be summarized at each visit by PAH background medication use, grouping subjects into monotherapy and combination therapy groups. The summary table will mimic that presented in the summary of study drug dosing by previous study, but will produce a separate summary table for each PAH background medication use group.

The summary of BID to TID transition will detail the number (percent) of subjects who completed this transition and who had to transition back to BID (if applicable), and descriptive statistics on the doses both before and after the transition by previous study and overall. All of these summaries will be provided by previous study and overall.

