## 11.2 ADVERSE EVENTS

Adverse event summaries will include treatment emergent AEs. Treatment emergent AEs include those reported during the parent study for those subjects who were treated with active drug during the parent study. For subjects treated with placebo during the parent study, only those AEs reported during the TDE-PH-304 study are considered treatment emergent.

The AEs will be coded using the Medical Dictionary for Regulatory Activities (MedDRA) and all summaries will utilize the preferred term (PT) and/or System Organ Class (SOC). The correspondence of raw AE terms to PTs and SOCs will be listed. All AEs and serious AEs will be listed by subject, including onset date/day, cessation date/day, verbatim term, PT, SOC, seriousness, severity, relationship to study drug, frequency, and action taken with study drug. The summaries of AEs will be provided by previous study and overall. The summaries of AEs, serious AEs, severe AEs, AEs reasonably or possibly related to study drug, and AEs leading to permanent discontinuation of study drug will include the number of subjects (percent of subjects) and number of events for each reported PT. The summary of AEs by body system will include the same statistics, but will group the PTs by their respective SOCs.

The summary of AEs by exposure will include the number of subjects (percent of subjects) and number of events for each reported PT, as well as the number of events per patient year of exposure. Note that only those subjects with calculated exposure will have AEs contributing to this summary.

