**12.2 LIST OF TABLES**

Table titles suggested here may be altered or edited as appropriate by the clinical data programmers while maintaining the original intent of the summary.

Table Number	Table Title
14.1.1	Summary of Subject Accountability
14.1.2	Summary of Disposition and Study Drug Exposure
14.1.3	Summary of Demographics
14.1.4	Summary of PAH History
14.1.5	Summary of Admission Criteria Violations
14.1.6.1	Summary of Study Drug Dosing by Previous Study and Overall
14.1.6.2	Summary of Study Drug Dosing by PAH Background Medication Use
14.1.6.3	Summary of BID to TID Transition
14.1.7.1	Summary of PAH Concomitant Medications Ongoing at Start of TDE-PH-304 Study
14.1.7.2	Summary of PAH Concomitant Medications Added During the TDE-PH-304 Study
14.1.7.3	Summary of PAH Medication Use by Class
14.1.7.4	Summary of Other Concomitant Medications
14.2.1.1	Summary of Six-Minute Walk Distance at Month 12 by Previous Study
14.2.1.2	Summary of Borg Dyspnea Score at Month 12 by Previous Study
14.2.1.3	Summary of Six-Minute Walk Distance at Month 12 by Treatment Assignment in Previous Study
14.2.1.4	Summary of Borg Dyspnea Score at Month 12 by Treatment Assignment in Previous Study
14.2.1.5	Summary of Six-Minute Walk Distance by PAH Medication Use
14.2.1.6	Summary of Borg Dyspnea Score by PAH Medication Use
14.2.1.7	Summary of Six-Minute Walk Distance by PAH Etiology
14.2.1.8	Summary of Six-Minute Walk Distance by Baseline WHO Functional Class
14.2.1.9	Summary of Six-Minute Walk Distance by Dosing Quartiles/ Tertiles
14.2.1.10	Summary of Six-Minute Walk Distance Achievement at Month 12
14.2.1.11	Summary of Six-Minute Walk Distance at Baseline by Achievement of At Least 380 Meters at Month 12

Table Number	Table Title
14.2.1.12	Summary of Clinical Events
14.3.1.1	Summary of Adverse Events
14.3.1.2	Summary of Adverse Events by System Organ Class
14.3.1.3	Summary of Serious Adverse Events
14.3.1.4	Summary of Serious Adverse Events Reasonably or Possibly Related to Study Drug
14.3.1.5	Summary of Adverse Events Reasonably or Possibly Related to Study Drug
14.3.1.6	Summary of Severe Adverse Events
14.3.1.7	Summary of Adverse Events Leading to Permanent Discontinuation of Study Drug
14.3.1.8	Summary of Disease Related Events
14.3.1.9	Summary of Adverse Events by UT-15C Exposure Time
14.3.2.1	Listing of Deaths
14.3.2.2	Summary of Deaths
14.3.2.3	Listing of Serious Adverse Events
14.3.4.1	Summary of Hematology Data

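### The cumulative adverse-event rate per patient-year in Table 14.3.1.9 can drift, or hide a late change in risk, because the early share of exposure changes between interims

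*SAP*

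**What the plan says.** SAP section 11.2 describes a summary of adverse events by exposure. For each preferred term it gives subjects, events, "as well as the number of events per patient year of exposure". The same section states: "The summaries of AEs will be provided by previous study and overall". No other stratification is named. SAP section 12.2 lists the table as 14.3.1.9, "Summary of Adverse Events by UT-15C Exposure Time".

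Numerator and denominator run over the same period. For events: "Treatment emergent AEs include those reported during the parent study for those subjects who were treated with active drug during the parent study". For exposure (SAP section 11.1): "For subjects treated with active drug during the parent study, exposure calculations will include their exposure during the parent study". Subjects on placebo in the parent study contribute only from their first active dose in TDE-PH-304.

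SAP section 5 provides for interim analyses to support submissions and "as frequently as yearly in order to continuously monitor the long-term safety of oral treprostinil in this ongoing study". SAP section 3 has visits at 3, 6, 12, 24 and 36 months of exposure, then yearly with no fixed end.

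Protocol section 3.2 says that ex-placebo subjects, and TDE-PH-202 subjects starting again at 0.25 mg BID, "must be contacted weekly by telephone (at a minimum) during the first 12 weeks of the open-label study". For everyone the minimum is then a monthly call. Protocol section 6.1.1 says that in general "the dose of study drug should be increased in 0.25 to 0.5 mg increments every 3 days", subject to tolerability, and sets no end to titration.

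**The concern.** Events divided by patient-years is an average over whatever exposure has accrued. It represents any one period of treatment only if the event rate, and the chance of recording an event, are about constant over time on drug. The design gives reasons to doubt this: frequent dose increases limited by side effects after starting, and weekly contact in the first 12 weeks for new starters.

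The table is regenerated as follow-up lengthens and new subjects enter, so the mix of early and late exposure in its denominator differs from one interim to the next. Movement in the rate may then reflect that mix rather than risk, and a real change in long-term risk may be diluted.

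The second and stated objective is long-term safety. No other planned adverse-event table separates early from late experience: the rest give cumulative subjects, percentages and events. Onset dates and days appear only in listings. Dosing, by contrast, is summarised at each visit, and clinical events have Kaplan-Meier curves.

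**Working it through.** **No figure to reproduce.** The documents state no adverse-event rate, patient-year total or dropout rate. The figure of about 900 subjects is an enrolment assumption.

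**Inputs from the documents.** Early period te = 12/52 = 0.231 year (Protocol section 3.2). Yearly interims (SAP section 5).

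**Assumptions.** Late rate 2.0 events per patient-year; early rate k times that, with k from 0.5 to 5; annual dropout 0%, 15% or 30%; several entry patterns. The late rate only sets the scale: relative drift depends on k and the early share.

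**Formula.** Let s(t) be the early share of accumulated patient-years at interim t. Then

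cumulative rate = 2.0 × [1 + (k − 1) × s(t)].

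If all subjects enter together, person-time per entrant between a and b years is PT(a,b) = (e^(−λa) − e^(−λb))/λ, with λ = −ln(1 − annual dropout), or b − a without dropout. Then s(t) = PT(0,te)/PT(0,t).

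**Early share, years 1 to 5, all entering together**

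| Dropout | 1 | 2 | 3 | 4 | 5 |
|---|---|---|---|---|---|
| 0% | 23.1% | 11.5% | 7.7% | 5.8% | 4.6% |
| 15% | 24.5% | 13.3% | 9.5% | 7.7% | 6.6% |
| 30% | 26.3% | 15.5% | 12.0% | 10.4% | 9.5% |

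**Cumulative rate, 15% dropout, late rate fixed at 2.0**

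| Early/late ratio k and entry | 1 | 2 | 3 | 4 | 5 |
|---|---|---|---|---|---|
| k = 0.5, together | 1.75 | 1.87 | 1.90 | 1.92 | 1.93 |
| k = 1, together | 2.00 | 2.00 | 2.00 | 2.00 | 2.00 |
| k = 2, together | 2.49 | 2.27 | 2.19 | 2.15 | 2.13 |
| k = 3, together | 2.98 | 2.53 | 2.38 | 2.31 | 2.26 |
| k = 5, together | 3.96 | 3.06 | 2.76 | 2.62 | 2.53 |
| k = 3, uniform entry over 5 years | 3.69 | 2.95 | 2.68 | 2.54 | 2.46 |
| k = 3, 300 at start and 600 spread over year 3 | 2.98 | 2.53 | 2.76 | 2.49 | 2.36 |

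Worked example, k = 3, year 1: 2.0 × (1 + 2 × 0.245) = 2.98. In the last row the year-3 value implies s = (2.76/2.0 − 1)/2 = 0.19, up from 0.13 at year 2, so the new wave raises the rate.

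**Masking.** Take k = 3, all entering together, 15% dropout, and a late rate that rises 30% after year 2, from 2.0 to 2.6. For t > 2:

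rate = [6 × PT(0,te) + 2 × PT(te,2) + 2.6 × PT(2,t)]/PT(0,t).

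Years 1 to 5 give 2.98, 2.53, 2.55, 2.56, 2.57. From year 2 to year 5 the cumulative rate moves 0.04, or 1.6%, while late risk is 30% higher.

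**Capture alone.** With a constant true rate of 2.0, full capture in the first 12 weeks and 60% afterwards, the cumulative rate is 1.40, 1.31, 1.28, 1.26, 1.25.

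**With bands.** When the late rate is constant and only the exposure mix moves, every band after month 3 shows 2.0 at every interim, whatever the ratio, entry pattern or dropout. In the masking example the bands beyond 24 months show 2.6 against 2.0 before. In the capture example the later bands show 1.2 throughout: stable, but still under-recorded.

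**The case against.** A reader might infer that the rate must fall at every yearly interim. The documents do not support that. It needs an early rate, or early capture, above the later one, and they give no rates by time on drug. It also needs a shrinking early share. Entry is by rollover from six named studies plus any further protocols, so a new wave can reverse the direction. With k = 1 there is no drift, and with k = 0.5 the rate rises.

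The early and late periods are also not cleanly separated. In TDE-PH-304 the 12 weeks of weekly calls cover only ex-placebo and restarting TDE-PH-202 subjects; for prior-active subjects early exposure enters through parent-study data. Titration has no fixed end, and weekly contact resumes for four weeks after a BID-to-TID change.

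A cumulative rate is a legitimate average, the study is descriptive and unpowered, and no formal comparison of rates between interims is planned. The table's title could be read as meaning bands of exposure time. SAP sections 1 and 8.1 leave room for further analyses, and onset days are listed.

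These points limit the predicted direction and size. They do not remove the gap. SAP section 11.2 defines only a cumulative rate, the title does not override it, and neither of the permissive sections commits to time bands. The columns by previous study hold the source of subjects fixed, but not time on drug. That the rate can rise as well as fall is itself a reason not to read it across interims.

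**Conclusion.** The point holds as a statement of what can happen: movement or stability of the cumulative rate between interims cannot be attributed to long-term risk, because the exposure mix changes as well. It rests on the assumption that events are more frequent or better captured early, which the design makes plausible but the documents do not quantify.

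The drift is largest while follow-up is short. With k = 3 and 15% dropout the fall is 15% from year 1 to year 2 (2.98 to 2.53) but only 5% from year 3 to year 5 (2.38 to 2.26); with k = 2 the latter is about 3% (2.19 to 2.13). In mature data the more serious consequence is masking: a 30% late increase leaves the illustrative rate almost flat. The planned table is valid as an overall average, and the change is a cheap improvement that serves a stated objective.

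**What to change.** In SAP section 11.2 and Table 14.3.1.9, add events, patient-years at risk and rate by time since first active dose, in bands of 0-3, >3-12, >12-24 and >24-36 months, then yearly beyond 36 months as data permit. A single open-ended last band would repeat the pooling problem. Show the bands overall for all preferred terms, and by previous study only for common terms or by system organ class. Keep the cumulative rate, and state that successive interims are read on the interval rates.

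The cost is programming, from onset and dosing dates already used. The downsides are a wider table and sparse cells for rare terms. Later bands describe only subjects still on drug, and they include re-titration after a TDE-PH-202 restart or a BID-to-TID change; both should be footnoted. Bands show where differences in capture fall but do not correct them.

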## 11.3 DISEASE RELATED EVENTS

The disease-related events reported during the TDE-PH-304 study will be listed, including subject number, previous study, and symptom. The summary will include the number (percent) of subjects who reported each symptom by previous study and overall.

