3.3.2.2 Adverse Event Assessment

Adverse event reporting instructions for protocols TDE-PH-202, TDE-PH-203, TDE-PH-205, TDE-PH-301, TDE-PH-302, and TDE-PH-308 will be followed in the open-label study. Adverse events will be reported continuously, as in protocols TDE-PH-202, TDE-PH-301, TDE-PH-302, and TDE-PH-308 and documented on the Case Report Form (CRF). Any AEs that were ongoing at the time of discharge from protocols TDE-PH-202, TDE-PH-203, TDE-PH-205, TDE-PH-301, TDE-PH-302, or TDE-PH-308 should be recorded as a part of the medical history in the open-label study. Section 9 and Appendix C provide the guidelines and definitions for recording of AEs.

For subjects transitioning from a BID to TID regimen, additional adverse event information will be collected via weekly phone contact for at least four weeks from the date of transition.

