9.1.3 Expected Adverse Event

Adverse events associated with progression of PAH:

An expected event that is related to the progression of a subject's PAH is defined in Appendix D, Part A. All events that occur during the course of the study that are included on this list and felt to be related to progression of disease by the Investigator should NOT be recorded as AEs in the CRF as the most relevant PAH symptoms will be evaluated and recorded as an efficacy endpoint and all other events will be captured as disease related events. If the event is either serious or unusual with respect to intensity, frequency, or duration, OR there is a reasonable possibility that it may have been caused by study drug, it must be recorded as an AE in the CRF.

Adverse events known to be associated with treprostinil therapy:

An expected AE for UT-15C is defined as any AE that is defined in terms of nature, severity, or frequency in the current Investigators' Brochure and in Appendix D, Part B. When an adverse event may be attributed to the progression of pulmonary hypertension or UT-15C SR (e.g., listed in both Parts A and B) it must be recorded as an AE in the CRF if the event is either serious or unusual with respect to intensity, frequency, or duration, OR there is a reasonable possibility that it may have been caused by study drug.

Expected events attributable to UT-15C (e.g., listed in Part B only) must always be recorded as AEs in the CRF.

If an event listed in Appendix D Part A or B occurs during the conduct of the trial, it will not give rise to submission of an expedited safety report despite being considered serious and possibly attributable to the study drug, unless the United Therapeutics Medical Monitor, responsible for assessing the case considers it to be unusual (e.g., more severe than expected) and therefore reportable. The data regarding such events will always be recorded in the clinical study database, regardless of reportability.

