#### **7 ANALYSIS POPULATIONS**

All available data from all subjects enrolled in the TDE-PH-304 study will be used as detailed in this analysis plan. Additionally, subjects who were treated with active drug during the parent study and who enrolled in the TDE-PH-304 study will have the data from the parent study included in the data analyses and listings for this study, as detailed in this SAP.

Subjects who were treated with placebo during the parent study and who enrolled in the TDE-PH-304 study will have baseline data only from the parent study included in the data analyses and listings for this study, as detailed in this SAP.

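### SAP 11.3 counts disease-related events only within TDE-PH-304, whereas AEs and exposure of subjects treated with active drug in the parent study start there, so Table 14.3.1.8 covers different parts of time on drug.

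*SAP*

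**What the plan says.** SAP 11.3 sets the window for disease-related events: "The disease-related events reported during the TDE-PH-304 study will be listed". Its summary (Table 14.3.1.8) gives the number and percent of subjects with each symptom, by previous study and overall, and names no other window.

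The neighbouring safety sections use a longer window for subjects treated with active drug in the parent study. On exposure, SAP 11.1 says: "For subjects treated with active drug during the parent study, exposure calculations will include their exposure during the parent study". On adverse events, SAP 11.2 says: "Treatment emergent AEs include those reported during the parent study for those subjects who were treated with active drug during the parent study". For placebo-parent subjects, "only those AEs reported during the TDE-PH-304 study are considered treatment emergent".

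SAP 7 has the general rule that active-parent subjects "will have the data from the parent study included in the data analyses and listings for this study", but qualifies it by the detail given elsewhere in the SAP. It therefore does not override 11.3.

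Protocol 9.1.3 determines which record an event enters. Events on the Appendix D Part A list that are "felt to be related to progression of disease by the Investigator should NOT be recorded as AEs in the CRF" go elsewhere: the most relevant PAH symptoms to an efficacy endpoint, while "all other events will be captured as disease related events". The same section requires an event to be recorded as an AE after all if it is serious, unusual in intensity, frequency or duration, or possibly caused by study drug.

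**The concern.** Under Protocol 9.1.3 the disease-related-event table is the counterpart of the AE tables: an ordinary progression symptom left out of one is meant to be found in the other. That works only if both start on the same day. For active-parent subjects they do not. An ordinary progression symptom on UT-15C SR in the parent study falls before the start of Table 14.3.1.8 and, if the parent study applied the same recording rule, was never an AE.

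Placebo-parent subjects have no such gap, because their first active dose is taken in TDE-PH-304. SAP 8.1 presents all summaries by previous study so that its impact can be examined. In Table 14.3.1.8 the columns would then differ partly because of the observation window. Long-term safety is a stated objective, and the early period on drug would be missing for one group and present for the other.

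**Working it through.** The documents give no figure on this point, so there is none to reproduce. The check sets the data windows side by side and then sizes the gap by illustration.

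**Windows**

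| Analysis | Active-parent subjects | Placebo-parent subjects |
|---|---|---|
| Exposure (SAP 11.1) | parent + 304 | 304 only |
| Treatment-emergent AEs (SAP 11.2) | parent + 304 | 304 only |
| Clinical events (SAP 10.2) | parent + 304 | parent data added only for active-parent subjects |
| Laboratory (SAP 11.5) | parent + 304 | parent + 304 |
| Disease-related events (SAP 11.3) | **304 only** | 304 only |

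For placebo-parent subjects, 304 only is all of their time on drug. For active-parent subjects it is not. SAP 11.4 also ties deaths to TDE-PH-304, but this loses nothing, since a subject who died in the parent study could not have enrolled.

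**Columns affected.** TDE-PH-202, 203 and 205 were open-label (Protocol 3.1), so the pooled 200-series column lacks the parent period for essentially everyone except the two de novo TDE-PH-301 subjects placed there by SAP 8. The pooled 301/308 column and the 302 column lack it only for subjects who received UT-15C SR. No allocation ratio is given, so that fraction cannot be stated.

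**Which events drop out**
1. Serious, unusual or possibly drug-caused progression events are AEs under Protocol 9.1.3 and, through SAP 11.2, are in the AE tables with parent data. Not lost.
2. Discontinuation for progression and added PAH therapy are clinical events under SAP 10.2, with parent data for active-parent subjects. Not lost.
3. The remaining progression events routed to disease-related events are in neither the AE tables nor Table 14.3.1.8, if the parent study used the 9.1.3 rule.

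**Did the parent studies use that rule?** Protocol 3.3.2.2 says: "Adverse event reporting instructions for protocols TDE-PH-202, TDE-PH-203, TDE-PH-205, TDE-PH-301, TDE-PH-302, and TDE-PH-308 will be followed in the open-label study". This implies a common rule but does not state that each parent study had the exclusion or a separate record of disease-related events. The Appendix D title, which refers to UT-15C SR clinical studies in the plural, points the same way.

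**Share of on-drug time outside the window.** Formula: parent weeks / total weeks on drug, with 12 months = 365.25/7 = 52.18 weeks. The 12-week Treatment Phase is documented for TDE-PH-202 only (Protocol 3.5).
- Month 6: 12/26.09 = 46%
- Month 12: 12/52.18 = 23%
- Month 24: 12/104.36 = 11.5%
- Month 36: 12/156.54 = 7.7%

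For assumed parent phases of 16 and 24 weeks, the month-12 share is 16/52.18 = 31% and 24/52.18 = 46%.

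**Effect on a subject percentage.** Table 14.3.1.8 counts subjects, and a subject whose symptom recurs in TDE-PH-304 is still counted. Under an assumed constant hazard, if P is the true month-12 percentage and T = 52.18 weeks, then λ = −ln(1 − P)/T and the percentage shown is 1 − exp(−λ(T − parent weeks)).

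| True P (assumed) | Shown, 12-week parent | Shown, 24-week parent (assumed) |
|---|---|---|
| 20% | 15.8% | 11.4% |
| 40% | 32.5% | 24.1% |
| 60% | 50.6% | 39.0% |

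For 12 weeks the relative shortfall is 4.2/20 = 21%, 7.5/40 = 19% and 9.4/60 = 16%, each below the 23% share of time.

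**The case against.** The strongest reply is that the key step rests on protocols not supplied. If a parent study recorded progression symptoms as AEs, SAP 11.2 already brings them into the AE tables and nothing is lost for that study. This stands as a condition on the point. It does not remove the difference in windows, which is in the SAP itself.

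Second, the window in 11.3 is stated openly, SAP 7 allows each section to set its own, disease-related events are not a listed endpoint, and no formal between-study comparison is planned. That limits the weight of the point. But the SAP gives no reason for the different window, and the table is still laid out by previous study.

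Third, eligibility works against a constant hazard. Subjects from 301, 302 or 308 who stopped UT-15C SR for clinical worsening are excluded, as are TDE-PH-202 iMTD subjects who worsened; TDE-PH-202 Dose Groups 1 and 2 may still enter under conditions. Enrolled active-parent subjects are therefore largely selected for not having stopped for worsening, and their parent-period event rate may be lower than later. This stands, and the illustrated shortfalls may be too large.

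Fourth, symptoms that a parent study recorded as an efficacy endpoint rather than as disease-related events would not be recovered by widening 11.3. This also stands.

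**Conclusion.** The point holds in a limited form. As written, SAP 11.3 observes active-parent and placebo-parent subjects over different parts of their time on drug. If the parent studies used the Protocol 9.1.3 rule, ordinary progression events of active-parent subjects in the parent period are in neither the AE tables nor Table 14.3.1.8. With a 12-week parent phase the uncovered share of on-drug time is 23% at month 12 and 8% at month 36. These figures are illustrations: the phase length is documented for one parent study, and the effect on subject percentages is not this share and may be smaller.

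Four stronger readings are tempting, and the documents do not support them:
- A reader might infer that all early progression events disappear. Serious, unusual or possibly drug-caused ones are AEs, and discontinuations for progression and added PAH therapy are in the clinical-event analyses.
- A reader might infer that 23% of disease events, or of affected subjects, are lost. The table counts subjects once per symptom, and the rate in the parent period is unknown.
- A reader might infer a wrong rate denominator. Table 14.3.1.8 has no patient-year denominator.
- A reader might infer that half of the subjects from the placebo-controlled studies are affected. No allocation ratio is given.

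This is a low-cost improvement to a descriptive safety table.

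**What to change.** Reword SAP 11.3 along these lines: *Disease-related events with onset in TDE-PH-304 will be listed and summarized; for subjects who received active drug in the parent study, those reported on active drug in that study will be added, using the window that Section 11.2 applies to treatment-emergent AEs.*

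Flag the study of origin in Listing 16.2.7.3. Check for each parent study whether disease-related events were collected separately. Where they were not, footnote the corresponding column of Table 14.3.1.8 and say where progression symptoms were recorded instead. If the TDE-PH-304-only window is intended, state the reason in 11.3 and footnote the table to say that the parent period of active-parent subjects is not covered.

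The cost is one SAP sentence, a footnote and some data integration. Parent AE data are already being combined, but disease-related events may sit in separate datasets and may not exist for every parent study. The disease-event percentages would rise slightly.
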